9.4.6 Duration of hospitalization (Day 1 - Day 29; measured in days)

The total number of days with recorded use will be the sum of all reported days, regardless of whether the days occur consecutively or in disjoint intervals. Results will be summarized by descriptive statistics including medians and quartiles by treatment arm and compared between treatment groups using Wilcoxon rank sum test.

Summaries of the results of the secondary analyses are displayed in Table 11.

Table 11. Clinical study RPL554-COV-201 analysis tables - Secondary Analyses.

Table #	Table Name	Table Contents
14.2.5	Time to recovery, Day 1 - Day 29	Overall and by Treatment group
14.2.6	Proportion of patients in recovery at Day 60, ITT	Overall and by Treatment group Day 1 – Day 7 Day 1 – Day 14
14.2.7	Proportion of patients with improvement of one category using the 7-point ordinal scale from Day 1, ITT	Overall and by Treatment group Day 1 – Day 7 Day 1 – Day 14 Day 1 – Day 29
14.2.8	Proportion of patients with improvement of two categories using the 7-point ordinal scale from Day 1, ITT	Overall and by Treatment group Day 1 – Day 7 Day 1 – Day 14 Day 1 – Day 29
14.2.9	All-cause mortality, ITT	Overall and by Treatment group At Day 29 At Day 60
14.2.10	Proportion of patients alive and not in respiratory failure (invasive mechanical ventilation or extracorporeal membrane oxygenation (ECMO) at Day 29, ITT	Overall and by Treatment group Day 1 – Day 7 Day 1 – Day 14
14.2.11	Summary of the proportion of patients re- hospitalized following initiation of study medication and subsequent discharge (over 60 days), ITT	Overall and by Treatment group
14.2.12	Duration of hospitalization from Day 1 (Day 1 - Day 29; measured in days), ITT	Overall and by Treatment group
14.2.13	Change from baseline in 7-point ordinal scale at Days 7, 14 and 29, ITT	Overall and by Treatment group Baseline – Day 7 Baseline – Day 14 Baseline – Day 29
14.2.14	Total time on supplemental oxygen (Day 1 - Day 29; measured in days), ITT	Overall and by Treatment group
14.2.15	Total time of non-invasive ventilation or high flow oxygen use (post-dose Day 1 - Day 29; measured in days).	Overall and by Treatment group
14.2.16	Summary of the proportion of patients with oxygen use at Days 7, 14 and 29, ITT	Overall and by Treatment group
14.2.17	Summary of the proportion of patients with non-invasive ventilation or high flow oxygen use at Days 7, 14 and 29), ITT	Overall and by Treatment group
14.2.18	Proportion of patients receiving invasive mechanical ventilation or extracorporeal membrane oxygenation (ECMO, 7-point ordinal scale criteria #6) at Days 7, 14 and 29, ITT	Overall and by Treatment group Day 1 – Day 7 Day 1 – Day 14 Day 1 – Day 29

pg. 25 Confidential

9.5 Safety Analysis

Safety endpoints include SAEs and AEs (Protocol Appendix 4). Adverse events will be analyzed using quantitative and qualitative measures.

Treatment-emergent adverse events will be summarized by treatment group for all AEs, related AEs, serious adverse events, deaths, adverse events leading to discontinuation of study medication or to withdrawal from study, adverse events of different severity and adverse events of different chronicity.

Treatment-emergent adverse events will be coded using MedDRA and summarized by system organ class and preferred term for each treatment group.

The time to the composite AE endpoint (death, SAE, severe AE or ET/W of treatment during first 29 days) will be compared between treatment groups using the log-rank test and difference between treatment arms will be expressed as a difference in proportions as measured by the Cochran Mantel-Haenzel (stratum)-weighted estimator based on the fitted logistic regression model

• If '0' events, proportions will be presented.

Summaries of the results of the safety analysis are displayed in Table 12.

Table 12. Clinical study RPL554-COV-201 analysis tables - Safety Analyses.

Table #	Table Name
14.3.1	Time to first composite AE (Safety Analysis Set)
14.3.2	Number/Proportion Treatment emergent adverse events summary (Safety Analysis Set)
14.3.3	Number/Proportion TEAEs by system organ class and preferred term (Safety Analysis Set)
14.3.4	Number/Proportion TEAEs leading to discontinuation of study treatment by system organ class and preferred term (Safety Analysis Set)
14.3.5	Number/Proportion TEAEs causally related to the study treatment by system organ class and preferred term (Safety Analysis Set)
14.3.6	Number/Proportion TEAEs by maximum severity by system organ class and preferred term (Safety Analysis Set)
14.3.7	Number/Proportion Serious TEAEs by system organ class and preferred term (Safety Analysis Set)
14.3.8	Number/Proportion Serious TEAEs causally related to the study treatment by system organ class and preferred term (Safety Analysis Set)
14.3.9	Number/Proportion Serious TEAEs by maximum severity by system organ class and preferred term (Safety Analysis Set)
14.3.10	Number/Proportion Serious TEAEs leading to discontinuation of study treatment by system organ class and preferred term (Safety Analysis Set)
14.3.11	Number/Proportion TEAEs with an outcome of death by system organ class and preferred term (Safety Analysis Set)

9.5.1 Deaths, Serious Adverse Events and other Significant Adverse Events Narratives will be provided for deaths and serious adverse events.

pg. 26 Confidential

9.5.2 Pregnancies

For any patients in the Safety population who become pregnant during the study, every attempt will be made to follow these patients to completion of pregnancy to document the outcome, including information regarding any complications with pregnancy and/or delivery.

9.6 Other or Exploratory Analyses

Proportion of patients in recovery, Day 1-7 and Day 1-14.

Proportion of patients alive and not in respiratory failure (invasive mechanical ventilation or extracorporeal membrane oxygenation (ECMO): Day 1- 7 and Day 1 - 14.

Description of the distribution of the 7-point ordinal scale outcomes using plots (e.g., stacked bar plots representing the proportion of patients in each category, by treatment arm, over time).

Descriptive summary of the number of days between hospital admission, positive PCR test (or as per hospital testing protocol) and randomization.

Proportion of total patients requiring any oxygen at randomization.

 For those that required oxygen, the mean/standard deviation or median/IQR for the oxygen amount (in FiO2).

Oxygen use while hospitalized and undergoing study treatment.

• Measurement of the oxygen requirement: compare the oxygen requirement (mean and median) for each arm using daily supplemental oxygen flow (L/min).

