4.2.1 Rationale for ensifentrine in treatment of COVID-19

In terms of clinical outcomes, Verona Pharma hypothesizes that ensifentrine treatment of patients with COVID-19 will effectively result in bronchodilation in patients, reducing symptoms of dyspnea and improve the patient's oxygen levels thus reducing the need for supplemental oxygen. Activity of ensifentrine related to reduction of viral-induced inflammation and CFTR stimulation may facilitate viral clearance more rapidly and help

prevent further clinical deterioration resulting from reduced oxygenation and secondary infections related to mucus hypersecretion. As such, the goal of ensifentrine treatment in patients with COVID-19 is to improve clinical status, facilitate recovery and prevent the progression of the disease leading to mechanical ventilation by allowing the patient to breathe better during the infection, to reduce the inflammation in the lung and facilitate patient recovery from COVID-19 infection.

Because ensifentrine provides bronchodilation via its inhibition of PDE3 and PDE4, anti-inflammatory effects following inhaled administration including the potential to decreased viral-induced inflammation, and bronchial cell CFTR stimulation, this pharmacologic therapy, delivered via pMDI, may serve as an innovative treatment for patients with COVID-19.

This study will expand our knowledge and understanding about how ensifentrine can be used to facilitate recovery or prevent deterioration in hospitalized, COVID-19 patients.

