7.1.1 Study specific discontinuation of study medication criteria

Patients should be withdrawn from study medication for the following reasons:

- If they experience a clinically significant progression of disease such as:
 - Kidney or liver or multi-organ failure
 - Need for mechanical ventilation
 - Stage 5, end stage kidney disease (GFR <15 mL/min)
 - ALT and/or AST increases to > 5 times upper limits of normal
- Pregnancy in a female patient
- If a patient who does not meet eligibility criteria is inadvertently randomized and received study medication

Other criteria that may or may not require permanent discontinuation of study medication include but are not limited to:

Adverse event, lack of efficacy, protocol deviation, non-compliance, study closed/terminated, investigator discretion, or patient withdrawal of consent.

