6 INVESTIGATIONAL PLAN

6.1 Overall Study Design and Plan

The purpose of this study is to evaluate the effect of ensifentrine on the proportion of patients hospitalized with COVID-19 infection with recovery over 29 days.

This is a single center, randomized, double-blind, parallel group, placebo-controlled study to determine the efficacy and safety of ensifentrine 2 mg BID administered via pMDI added on to SoC treatment for COVID-19 infection compared to patients receiving SoC plus placebo.

Patients 18 to 80 years of age must be hospitalized with a confirmed diagnosis of SARS-CoV-2 infection confirmed by PCR test and displays at least one of the following: Respiratory rate greater than 24, new cough, new atypical chest pain, new dyspnea, oxygen saturation <97% at rest, chest x-ray with new changes consistent with COVID-19 related airspace disease.

Patients meeting criteria for inclusion and none of the criteria for exclusion at randomization will be randomized to receive study medication within 4 days of hospital admission until hospital discharge or up to 29 days of treatment, whichever comes first. Patients will be randomized 2:1 to receive one of the following study treatments:

- Treatment Arm 1 (n=30): Blinded ensifentrine (2 mg) pMDI BID + Standard of Care treatment for COVID-19 infection
- Treatment Arm 2 (n=15): Blinded placebo pMDI BID + Standard of Care treatment for COVID-19 infection

Randomized patients will receive blinded ensifentrine or placebo twice daily, approximately 12 hours apart in the morning and evening, through 29 days or until discharge from hospital, whichever is first. Patients will self-administer 4 actuations (puffs) pMDI observed by study staff at each dosing event.

During the treatment period, patients will undergo all assessments and procedures as outlined in the schedule of activities until hospital discharge. Patients completing treatment will complete a study contact (telephone or visit as required) within 4 to 10 days of discharge or early withdrawal. All enrolled patients will complete a telephone contact 26 to 32 days (Day 29) and 55-65 days (Day 60) following receipt of 1st dose of study medication for assessment of clinical status via the 7-point ordinal scale, need for re-hospitalization and vital status.

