8.5 Missing Data

All attempts will be made to collect all data per protocol.

 The patients withdrawn from treatment will be followed up regarding their status according to the 7-point ordinal scale at Day 29 as far as possible (exceptions for patients with withdrawn consent or lost to follow-up) and this data will be the primary source for handling missing data in the study.

Any data point that appears to be erroneous or inexplicable based on clinical judgment will be investigated as a possible outlier.

• If data points are identified as outliers, sensitivity analyses may be performed to examine the impact of including or excluding the outliers. Any substantive differences in these analyses will be reported.

For survival analyses, patients with death as outcome will be censored at Day 29 (Day 60), unless the required event was reached prior to death. Patients who are lost to follow-up or terminate the study prior to Day 29 (Day 60) for other reason than death and prior to observing/experiencing the event will be censored at the time of their last observed assessment.

The only time to event analyses is the time to recovery.

For secondary endpoint analyses, the following imputation rules will be used for patients who are lost to follow-up, terminate early from the study, or do not have further outcome data available after discharge for any reason than death:

- Patients with no data collected at the actual time point of interest for other reason than
 death, the last assessment of their status prior to this time point will be used as a
 representative for that time point. Especially, if the patient's clinical status scale is 1 or 2
 at the last observed assessment, then the patient will be considered to be recovered
 through Day 29.
- For endpoints assessing total time (oxygen or non-invasive ventilator care), the status for patients with no data collected for other reason than death, will be assumed unchanged from last assessment of the score up to last day in the definition of the endpoint (Day 29). Thus, no extra days will be added for patients without oxygen or patients without non-invasive ventilator care at last assessment.
- Patients that die in the study will be handled as worst case in all the analyses, that is they are considered to be on oxygen need, non-invasive and invasive mechanical ventilator need for all time points following the death.

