9.4.2.1 Sub-sets based on post-randomization outcome

Descriptive summaries of the proportion of patients as well as the duration of the worsening following initiation of study medication will be provided for these endpoints:

- Proportion of patients needing re-hospitalization (post-dose Day 1 Day 60).
 - Applies to the sub-set of patients that were randomized, treated with study medication and discharged from the hospital alive then re-admitted to the hospital for COVID-19 related treatment.
- Proportion of patients and duration of new oxygen use (post-dose Day 1 Day 29; measured in days).
 - Applies to the sub-set of patients that were randomized and treated with study medication but then had a new need for supplemental oxygen (score worsened to 4, 5 or 6).
 - Or those which improved during hospitalization (to 3) and then their clinical status worsened again (to 4, 5 or 6).
- Proportion of patients and duration of new non-invasive ventilation or high flow oxygen use (post-dose Day 1 - Day 29; measured in days).
 - Applies to the sub-set of alive patients that were randomized and treated with study medication but then had a new need for non-invasive ventilation or highflow oxygen use (score worsened to 5 or 6).
 - Or those which improved during hospitalization (to 3 or 4) and then their clinical status worsened again (to 5 or 6)

The total number of days with recorded use will be the sum of all reported days, regardless of whether the days occur consecutively or in disjoint intervals.

9.4.3 Change from baseline in 7-point ordinal scale (Days 7, 14 and 29).

Change from baseline in 7-point ordinal scale will be compared between treatments using ANCOVA models with treatment and COVID disease severity state as factors and baseline as a covariate. Estimated treatment difference with 95% confidence intervals and associated 2-sided p-value will be given. Sub-group analysis will only be performed for sub-groups with a minimum size.

9.4.4 Total time on supplemental oxygen (Day 1 - Day 29; measured in days).

The total number of days with recorded use will be the sum of all reported days, regardless of whether the days occur consecutively or in disjoint intervals. Results will be summarized by descriptive statistics including medians and quartiles by treatment arm and compared between treatment groups using Wilcoxon rank sum test. Patients that do not reach the specified score on any day will be counted as 0 days.

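### SAP 9.6 compares oxygen flow only in patients still in hospital and on study drug; treatment decides who they are, so a real benefit can be masked and, in some settings, reversed

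*SAP*

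**What the plan says.** SAP 9.6 lists an item headed "Oxygen use while hospitalized and undergoing study treatment". Under it, the plan is to "compare the oxygen requirement (mean and median) for each arm using daily supplemental oxygen flow (L/min"). No test, denominator, method of combining days or value after discharge is given.

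Three other places decide who is in that set and what happens to those who leave:

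- SAP 6.1: dosing runs "through 29 days or until discharge from hospital, whichever is first", so discharge ends membership.
- Protocol 7.1.1: among the progression events for which study medication should be withdrawn is "Need for mechanical ventilation", so ventilated patients leave too.
- SAP 8.5: the imputation rules open with "For secondary endpoint analyses, the following imputation rules will be used for patients who are lost to follow-up". One bullet is broader: "Patients that die in the study will be handled as worst case in all the analyses". It then defines worst case as being in need of oxygen and ventilation, not as a number of L/min.

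Oxygen is also analysed in other ways. SAP 9.4.4 compares total days on oxygen in ITT patients ("Patients that do not reach the specified score on any day will be counted as 0 days"), and Table 5 counts home oxygen. SAP 9.4.2 covers proportions on oxygen and on non-invasive support at Days 7, 14 and 29. SAP 9.4.3 covers change in the ordinal score, and Figure 4 shows oxygen need by day.

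**The concern.** The sponsor's hypothesis in Protocol 4.2.1 is that the drug will "improve the patient's oxygen levels thus reducing the need for supplemental oxygen". Protocol 4.3 says the pilot is meant to read trends across endpoints. Flow in L/min is the only between-arm measure that grades need within ordinal category 4 (any supplemental oxygen). The SAP's own shells (Tables 14.1.5a and 14.1.5b) place 44 of 45 patients in that category at baseline.

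Leaving hospital is also the recovery event of the primary endpoint. Any effect on the primary endpoint therefore changes who is left in the flow comparison. If ensifentrine sends milder patients home sooner, its remaining patients are on average sicker and their mean flow rises. If an arm loses its sickest patients to ventilation or death, its mean flow falls. Either way the arms are compared in different remnants of the randomized groups, and the trend can understate or misdirect the message on amount of oxygen.

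**Working it through.** The documents give no flow values, no effect size and no power, so there is no plan figure to reproduce. All flow inputs below are assumptions; the allocation (30 v 15) is from the plan. Flow after discharge is set to 0 in the all-randomized columns, which ignores home oxygen.

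**1. Hand case, one day, 10 patients per arm.**

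- Placebo: 4 home, 4 at 1 L/min, 2 at 6 L/min. In hospital: (4×1 + 2×6)/6 = 16/6 = 2.7. All ten: 16/10 = 1.6.
- Ensifentrine: the four at 1 L/min are home as well, 2 at 6 L/min. In hospital: 12/2 = 6.0. All ten: 12/10 = 1.2.

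The sign flips. The case is extreme (8 of 10 v 4 of 10 home) and shows only the mechanism. The other exit works the opposite way: if the two placebo patients at 6 L/min were ventilated and stopped study drug, the mean of those left would fall from 2.7 to 4/4 = 1.0, although the arm had got worse.

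**2. Two-class mixture.** Half of each arm needs 2 L/min and half 6 L/min. A fraction h of the milder half is home, and the drug changes nobody's flow while they stay.

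- In-hospital mean = [0.5(1−h)×2 + 0.5×6] / [0.5(1−h) + 0.5] = (8−2h)/(2−h).
- All-randomized mean = 4−h.

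| h placebo v ensifentrine | In hospital (L/min) | Difference | All randomized | Difference |
|---|---|---|---|---|
| 0.3 v 0.5 | 4.35 v 4.67 | +0.31 | 3.70 v 3.50 | −0.20 |
| 0.3 v 0.7 | 4.35 v 5.08 | +0.72 | 3.70 v 3.30 | −0.40 |
| 0.5 v 0.7 | 4.67 v 5.08 | +0.41 | 3.50 v 3.30 | −0.20 |

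Differences are ensifentrine minus placebo, from unrounded means; plus is against the drug.

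**3. Simulation at trial size.** 3,000 trials per setting, 30 v 15 patients. Starting flow is lognormal (median 4 L/min, log-SD 0.5), with a linear fall of median 0.35 L/min per day. Discharge comes at or below 0.5 or 1.0 L/min, after at least 3 days. The drug speeds the fall by 1.3 to 2.0 times. Median placebo stay is about 9 to 11 days, against the 10 to 13 days for survivors cited in Protocol 4.3.

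| Who benefits | Summary of flow | In hospital, difference | All randomized, difference |
|---|---|---|---|
| Milder patients only | Day 7 mean | +0.28 to +0.84 | −0.13 to −0.33 |
| Milder patients only | Pooled patient-days | +0.14 to +0.26 | −0.02 to −0.10 (Days 1–29) |
| Milder patients only | One mean per patient | −0.02 to +0.02 | n/a |
| Everyone equally | Day 7 mean | −0.10 to −0.29 | −0.50 to −1.32 |
| Everyone equally | Pooled patient-days | −0.05 to +0.02 | −0.27 to −0.62 (Days 1–29) |
| Everyone equally | One mean per patient | −0.03 to +0.01 | n/a |

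When only milder patients benefit, the Day 7 in-hospital mean is higher on ensifentrine in 63% to 83% of trials. With all randomized patients kept in, it is higher in 34% to 44%, so chance alone is considerable at this size.

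**4. Dependence on the day.** A second model uses an exponential fall (mean log decline 0.12 per day, SD 0.10), sped up 1.3 times in recovering patients only, with 400,000 patients per arm. It gives in-hospital means, placebo v ensifentrine, of 3.15 v 3.42 at Day 10 and 3.76 v 4.29 at Day 14. All-randomized means are 2.00 v 1.76 and 1.86 v 1.72. A recoding with slightly different timing shows the early days still favour the drug (Day 3: 3.64 v 3.43; Day 7: 2.88 v 2.78), a tie at Day 8, and reversal by Day 10 (3.03 v 3.21). Its per-patient means are 3.05 v 3.03. If every patient gains the same absolute amount, the second model shows no reversal.

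**The case against.** The strongest reply is about weight. This is the last bullet of an exploratory section in an unpowered pilot. It has no named test, no confidence interval and no numbered table, and no decision hangs on it. That stands and limits the priority.

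A reader might infer that the plan's whole examination of oxygen need is biased. The documents do not support that: days on oxygen, proportions on oxygen and the ordinal score are all analysed in ITT patients, with discharged patients kept in. The problem is confined to the amount of oxygen.

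A reader might also infer that an effective drug will look harmful here. That is too strong. SAP 9.6 does not say whether flow is averaged by day, over patient-days or per patient, and reversal depends on that choice, on the day, and on who responds. The example shell for last day on study drug (Table 14.2.2) lists only Days 2 to 11, so a Day 14 on-drug comparison may have few or no patients.

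It can be said that the restriction itself is uncertain, because in SAP section 14 the flow line stands apart from the in-hospital item. In 9.6, which governs, it is nested under that item. Finally, the death rule in 8.5 may be read as reaching 9.6. Even so, it yields a state of need, not a flow, and says nothing on flow for discharged or ventilated patients.

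**Conclusion.** The concern holds in limited form. Followed as written, SAP 9.6 compares amount of oxygen in a set selected by outcome, and no other rule repairs it. A true benefit can be masked. Under assumed flows it is reversed, by about 0.3 to 0.8 L/min at Day 7 in the trial-size simulation, when milder patients gain most and flow is averaged by day; pooling patient-days gives a smaller reversal of about 0.1 to 0.3. With a uniform benefit, or one mean per patient, the benefit mostly disappears without changing sign. An arm with more ventilation or death can conversely look better. These sizes are illustrative, since the documents supply no flow data. Priority is low to moderate.

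**What to change.** In SAP 9.6, compare oxygen requirement on fixed days (for example Days 3, 7 and 14) in all randomized patients, on or off study drug, by Wilcoxon rank-sum test. Rank from best to worst:

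1. discharged without home oxygen;
2. in hospital on room air;
3. supplemental oxygen, ordered by L/min, with patients discharged on home oxygen at a stated rank within this group;
4. high-flow oxygen or non-invasive ventilation;
5. invasive ventilation or ECMO;
6. death.

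Home oxygen needs its own place because SAP Table 5 counts it as supplemental oxygen; ranking every discharged patient lowest would contradict that. Take home-oxygen status from the discharge and follow-up eCRFs, and state that last status is carried forward as in SAP 8.5.

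If in-hospital flow in L/min is also shown, label it descriptive, print the number remaining per arm and day, and make no between-arm comparison.

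The cost is SAP wording and one reprogrammed exploratory table. Protocol 8.1 and 8.1.4 already provide for daily recording of oxygen therapy and ventilation to discharge, Day 29 or withdrawal of consent, whether or not dosing continues. The protocol does not name L/min as a data item, although SAP 9.6 presumes it, so confirm that it is on the eCRF. The downside is that the result is a rank comparison and no longer a mean in L/min.

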8.1.2 Categorizing COVID-19 disease severity

Categorization of PCR positive COVID-19 disease severity will be in accordance with the FDA’s document: COVID-19: Developing Drugs and Biological Products for Treatment or Prevention Guidance for Industry (May 2020). Patients with Critical Disease would meet exclusion criteria and not eligible for participation.

- **Mild** disease (meeting all inclusion and no exclusion criteria): Symptoms of mild illness that could include fever, cough, sore throat, malaise, headache, muscle pain, gastrointestinal symptoms, without shortness of breath or dyspnea and no clinical signs indicative of moderate, severe, or critical severity.
- **Moderate** disease (meeting all inclusion and no exclusion criteria): could include any symptom of mild illness or shortness of breath with exertion. Clinical signs suggestive of moderate illness, such as respiratory rate ≥ 20 breaths per minute,

saturation of oxygen (SpO₂) > 93% on room air at sea level, heart rate ≥ 90 beats per minute and no clinical signs indicative of severe or critical severity.

- **Severe** disease (meeting all inclusion and no exclusion criteria): could include any symptom of moderate illness or shortness of breath at rest, or respiratory distress. Clinical signs indicative of severe systemic illness, such as respiratory rate ≥ 30 per minute, heart rate ≥ 125 per minute, SpO₂ ≤ 93% on room air at sea level or PaO₂/FiO₂ < 300 and no criteria of critical severity.
- **Critical** disease: evidence of critical illness, defined by at least one of the following: 1) respiratory failure defined based on resource utilization requiring at least one of the following: endotracheal intubation and mechanical ventilation, oxygen delivered by high-flow nasal cannula (heated, humidified, oxygen delivered via reinforced nasal cannula at flow rates > 20 L/min with fraction of delivered oxygen ≥ 0.5), noninvasive positive pressure ventilation, ECMO, or clinical diagnosis of respiratory failure (i.e., clinical need for one of the preceding therapies, but preceding therapies not able to be administered in setting of resource limitation); 2) shock (defined by systolic blood pressure < 90 mm Hg, or diastolic blood pressure < 60 mm Hg or requiring vasopressors); or 3) multi-organ dysfunction/failure.

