8.1.3 Vital sign assessment

Vital signs will be assessed and recorded each morning at approximately the same time of a given study day.

Vital signs to be assessed and recorded include: respiration rate (breaths per minute), oxygen saturation, supplemental oxygen use (yes/no), fraction of inhaled oxygen (FiO₂), sternal capillary refill time, body temperature, dehydration, blood pressure, heart rate (beats per minute and level of consciousness graded on the AVPU scale (Alert, Verbal = voice response present, Pain = pain response present, Unresponsive) (worst score on the assessment day for each).

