6.3.1 Inclusion Criteria

- Capable of giving informed consent indicating that they understand the purpose of the study and study procedures and agree to comply with the requirements and restrictions listed in the informed consent form and in this protocol.
- Patient must be at least 18 years of age and less than or equal to 80 years of age at the time of informed consent.
- Males are eligible to participate or females of non-childbearing potential or WOCBP who
 have a negative pregnancy test at screening are eligible to participate. WOCBP and
 female partners of male participants agree to either abstinence or use at least one
 primary form of highly effective contraception not including hormonal contraception from
 the time of screening through Day 60 following the first dose of study medication
 (Protocol Appendix 5).
- Clinical status consistent with 3, 4 or 5 on the 7-point ordinal scale AND the patient requires to be hospitalized for at least 72 hours following randomization:
 - 3. Hospitalized, not requiring supplemental oxygen, but requiring ongoing medical care;
 - 4. Hospitalized, requiring any supplemental oxygen; or
 - 5. Hospitalized, requiring non-invasive ventilation or use of high flow oxygen devices.
- Admission to hospital AND have a confirmed diagnosis of severe acute respiratory syndrome coronavirus (SARS-COV-2) infection confirmed by polymerase chain reaction (PCR) test (or as per hospital testing protocols) AND displays at least one of the following:
 - Respiratory rate > 24 breaths per minute,
 - new cough,
 - new atypical chest pain,
 - new dyspnea,
 - oxygen saturation < 97% at rest,
 - or chest x-ray with new changes consistent with COVID- related airspace disease.
- Capable of complying with all study restrictions and procedures including ability to use the pMDI correctly.

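### SAP 9.6 averages on-treatment oxygen as L/min pooled over devices while baseline oxygen is in FiO2, so the planned arm mean (not the median) partly measures the device; a minor, exploratory point

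*SAP*

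**What the plan says.** SAP 9.6, under "Other or Exploratory Analyses", has two neighbouring items on the amount of oxygen.

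- At randomization: "For those that required oxygen, the mean/standard deviation or median/IQR for the oxygen amount (in FiO2". Shell Table 14.1.6 also shows baseline supplemental oxygen as FiO2.
- On treatment, in hospital: "compare the oxygen requirement (mean and median) for each arm using daily supplemental oxygen flow (L/min". The shell section at the end of the SAP repeats both items with the same units.

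Neither document converts one unit to the other, splits the on-treatment summary by device, or says how daily values are combined within a patient. None gives a flow value for room air or non-invasive ventilation.

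More than one device can occur. Score 5 on the ordinal scale is an eligible category: "Hospitalized, requiring non-invasive ventilation or use of high flow oxygen devices". Protocol 8.1.2 describes high-flow oxygen by two settings: "oxygen delivered via reinforced nasal cannula at flow rates > 20 L/min with fraction of delivered oxygen ≥ 0.5".

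The documents disagree on whether daily FiO2 is collected. Protocol 8.1.3 includes "fraction of inhaled oxygen (FiO₂") among the vital signs recorded each morning. SAP Table 5 places it among the optional parameters, and the vital-sign list under the protocol's schedule of activities has only a yes/no item for supplemental oxygen. Protocol 8.1.4 separately has oxygen therapy details, high-flow use and non-invasive ventilation recorded daily.

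**The concern.** Litres per minute describes how a device is set. Among patients on the same low-flow device it is a workable index of oxygen requirement. Across devices it is not, because a high-flow system runs at a much larger gas flow whose oxygen fraction is chosen separately. A mean pooled over devices can jump when a patient changes device, by an amount that need not match the change in requirement.

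The arms are small and unequal (30 and 15), so the same event shifts the placebo mean twice as far as the ensifentrine mean. Shell Tables 14.1.5a and 14.1.5b show one patient at baseline score 3 and 44 of 45 at score 4. High-flow days would then be escalations after baseline, perhaps few, and a mean is sensitive to a few large values.

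Reducing the need for supplemental oxygen is a stated hypothesis (SAP 5), and the pilot may inform future studies (SAP 8.2). A device-driven mean could mislead a reader planning the next trial.

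**Working it through.** The plan states no expected value, SD or power for this item, so there is no figure to reproduce. The check is how far one patient moves the planned summaries.

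**Inputs.** Arm sizes of 30 and 15 are from SAP 6.1. The flows are assumptions: low flow 3 L/min (range 2 to 6) and high flow 40 L/min (range 20 to 60). The documents give only the threshold of more than 20 L/min. All patients in the arm are taken to be in hospital and on oxygen that day.

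**Step 1: mean flow on one day.** Shift = (high flow − low flow) / n.

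| Others at 3 L/min, one patient at | n = 15 | n = 30 |
|---|---|---|
| 20 L/min | 3.0 to 4.13 (+38%) | 3.0 to 3.57 (+19%) |
| 40 L/min | 3.0 to 5.47 (+82%) | 3.0 to 4.23 (+41%) |
| 60 L/min | 3.0 to 6.80 (+127%) | 3.0 to 4.90 (+63%) |

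For example, (40 − 3)/15 = 2.47 and 2.47/3 = 82%. Over the full assumed ranges the shift is +0.9 to +3.9 L/min (16% to 193%) at n = 15 and +0.5 to +1.9 (8% to 97%) at n = 30. With only 5 patients still in hospital, the 3-to-40 case gives 37/5 = +7.4 L/min.

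**Step 2: median.** It stays at the low-flow value in every scenario. With 15 low-flow values spread from 1 to 6 L/min (mean 3.2, median 3), changing one 6 to 40 takes the mean to 5.47 and leaves the median at 3.

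**Step 3: averaging within patient first.** Over 7 days with k days on high flow, shift = 37 × (k/7) / n.

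| High-flow days of 7 | n = 15 | n = 30 |
|---|---|---|
| 1 | 0.35 L/min | 0.18 L/min |
| 3 | 1.06 | 0.53 |
| 7 | 2.47 | 1.23 |

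The SAP does not say whether Step 1 or Step 3 is what it intends.

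**Step 4: what a flow reading means.** Taking room air as 0.21, added oxygen = flow × (FiO2 − 0.21)/0.79. At 20 L/min this is 2.3 L/min at FiO2 0.3, 7.3 at 0.5 and 20 at 1.0. One reading covers a nearly ninefold range (20/2.3). Within the protocol's high-flow definition (0.5 and above) the range is about 2.7-fold (20/7.3).

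**Step 5: the same event in FiO2.** Assume 3 L/min corresponds to 0.32, a conversion that is not in the documents. One patient going to 0.5 raises the mean by 0.18/15 = 0.012 (4%) at n = 15 and 0.006 (2%) at n = 30. Going to 1.0 raises it by 14% and 7%. As excess over room air (0.32 − 0.21 = 0.11), the rises are 11% and 5% at 0.5, and 41% and 21% at 1.0. FiO2 thus responds to the delivered fraction and does not change when only the flow setting changes.

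**The case against.** The strongest reply is that little rests on this item. It is the last bullet of an exploratory section, names no test or model, and has no entry in SAP Table 11. Oxygen need is already covered by secondary endpoints that do not use L/min: total time on oxygen, total time on non-invasive ventilation or high flow, and the proportions on oxygen or ventilation at Days 7, 14 and 29. SAP 8.5 gives those endpoints rules for ventilation and death. All of this stands.

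Four stronger readings are tempting, and the documents do not support them.

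- A reader might infer that one patient can decide the comparison. Only the mean is exposed. The median is planned beside it, and a gap between the two would itself show the skew.
- A reader might infer that escalation to invasive ventilation turns days into missing values and flatters an arm. SAP 9.6 limits the item to days on study treatment, and protocol 7.1.1 lists the need for mechanical ventilation among the reasons for withdrawal from study medication. Those days largely fall outside by scope, whatever the unit.
- A reader might infer that a planned change from baseline cannot be computed. None is planned for oxygen amount. The mismatch only stops the two summaries from being read side by side, and flow at baseline may exist in the treatment records.
- A reader might infer that FiO2 is almost immune to one patient. The 4% and 2% in Step 5 come from fixing FiO2 at 0.5, the minimum in the protocol's definition. On the excess scale at FiO2 1.0, the rise (41% and 21%) is about the same as that of flow at 20 L/min (38% and 19%).

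It is also fair that, with nearly all patients starting at score 4, most FiO2 values would be converted from L/min. For low-flow days the change is largely one of scale; the gain is on high-flow and non-invasive ventilation days.

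**Conclusion.** The point holds as a minor one. The pooled mean in L/min does not measure oxygen requirement consistently once high-flow or non-invasive ventilation days enter it, and it is not on the scale used at randomization. Its size depends on assumed flows and on an aggregation rule that the SAP does not give: for one patient at 40 L/min among others at 3 L/min, 82% (n = 15) or 41% (n = 30) on a single day. If seven days are averaged and only one is on high flow, the shift at n = 15 falls to 0.35 L/min, or 12% of 3. The median does not move in any scenario checked. Primary and secondary results are unaffected.

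**What to change.** First reconcile protocol 8.1.3 with SAP Table 5 and the schedule of activities on whether daily FiO2 is collected, and check what was actually captured.

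If it was reliably captured, amend SAP 9.6 so that on-treatment oxygen amount is summarised as daily FiO2, the scale used at randomization:

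- room air is 0.21;
- the set FiO2 is used on high-flow and non-invasive ventilation days;
- one conversion, prespecified in the SAP, is used for low-flow devices;
- the median is the main summary, with the mean beside it;
- a stated rule combines days within a patient.

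If it was not, report L/min for low-flow days only, give the number of high-flow and non-invasive ventilation days separately by arm, and do not pool devices.

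In either case, say that days after withdrawal from study medication, including invasively ventilated days, stay outside this on-treatment summary unless its scope is explicitly changed.

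The cost is SAP wording, one conversion table and a check of the eCRF, with no new data if FiO2 was captured. The downside is that FiO2 on a low-flow cannula is estimated, not measured.
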